1 OVERVIEW

Study Title:

HIV Testing at Family Planning Clinics in Mombasa County, Kenya: A Cluster-Randomized Trial comparing the Systems Analysis and Improvement Approach (SAIA) to Usual Procedures

1.1 Home institution. Identify the home institution of the lead researcher as listed on the IRB application. Provide any helpful explanatory information.

In general, the home institution is the institution (1) that provides the researcher's paycheck and that considers him/her to be a paid employee, or (2) at which the researcher is a matriculated student. Scholars, faculty, fellows, and students who are visiting the UW and who are the lead researcher: identify your home institution and describe the purpose and duration of your UW visit, as well as the UW department/center with which you are affiliated while at the UW.

Note that many UW clinical faculty members are paid employees of non-UW institutions.

*The UW IRB provides IRB review and oversight for only those researchers who meet the criteria described in the **POLICY: Use of the UW IRB**.*

University of Washington

1.2 Consultation history. Have you consulted with anyone at HSD about this study?

It is not necessary to obtain advance consultation. If you have: answering this question will help ensure that the IRB is aware of and considers the advice and guidance you were provided.

No

Yes

→ If yes, briefly describe the consultation: approximate date, with whom, and method (e.g., by email, phone call, in-person meeting).

1.3 Similar and/or related studies. Are there any related IRB applications that provide context for the proposed activities?

Examples of studies for which there is likely to be a related IRB application: Using samples or data collected by another study; recruiting subjects from a registry established by a colleague's research activity; conducting Phase 2 of a multi-part project, or conducting a continuation of another study; serving as the data coordinating center for a multi-site study that includes a UW site.

Providing this information (if relevant) may significantly improve the efficiency and consistency of the IRB's review.

No

Yes

→ If yes, briefly describe the other studies or applications and how they relate to the proposed activities. If the other applications were reviewed by the UW IRB, please also provide: the UW IRB number, the study title, and the lead researcher's name.

1.4 Externally-imposed urgency or time deadlines. Are there any externally-imposed deadlines or urgency that affect your proposed activity?

HSD recognizes that everyone would like their IRB applications to be reviewed as quickly as possible. To ensure fairness, it is HSD policy to review applications in the order in which they are received. However, HSD will assign a higher priority to research with externally-imposed urgency that is beyond the control of the researcher. Researchers are encouraged to communicate as soon as possible with their HSD staff contact person when there is an urgent situation (in other words, before submitting the IRB application). Examples: a researcher plans to test an experimental vaccine that has just been developed for a newly emerging epidemic; a researcher has an unexpected opportunity to collect data from students when the end of the school year is only four weeks away.

HSD may ask for documentation of the externally-imposed urgency. A higher priority should not be requested to compensate for a researcher's failure to prepare an IRB application in a timely manner. Note that IRB review requires a certain minimum amount of time; without sufficient time, the IRB may not be able to review and approve an application by a deadline.

No

Yes → If yes, briefly describe the urgency or deadline as well as the reason for it.

1.5 Objectives Using lay language, describe the purpose, specific aims, or objectives that will be met by this specific project. If hypotheses are being tested, describe them. You will be asked to describe the specific procedures in a later section.

If your application involves the use of a HUD "humanitarian" device: describe whether the use is for "on-label" clinical patient care, "off-label" clinical patient care, and/or research (collecting safety and/or effectiveness data).

Our overarching objective is to assess the effectiveness, costs, and budget impact of implementing this **systems analysis and improvement approach (SAIA)** to increase HIV testing in FP clinics in Mombasa County.

Our specific aims are as follows:

AIM 1: To conduct a cluster-randomized trial comparing the effect of the SAIA approach versus usual procedures on rates of HIV testing in first-time attendees at 12 intervention versus 12 control FP clinics in Mombasa County, Kenya.

HYP 1: After one year of study team support implementing SAIA vs. usual procedures, a higher proportion of first-time FP clinic attendees will be tested for HIV at intervention compared to control facilities

AIM 2: To determine whether the SAIA training results in a lasting effect, we will compare HIV testing rates for first-time FP clinic attendees in SAIA intervention versus control facilities after an additional year, during which FP clinics in the intervention arm will be encouraged to continue to use the SAIA tools with minimal support from the study team. The Mombasa County Ministry of Health will take ownership of implementation during this phase.

HYP 2: After an additional year with minimal support from the study team, there will continue to be significantly higher rates of HIV testing in first-time FP clinic attendees at intervention compared to control facilities.

AIM 3: To estimate the incremental cost and budget impact of applying SAIA versus standard of care.
Using an activity-based approach, we will perform a costing analysis, estimating cost per new HIV diagnosis, both

during active support from the study team and after a period without active support. We will also estimate cost to scale up, and conduct a budget impact analysis from a Department of Health (DOH) perspective.

1.6 Study design. Provide a one-sentence description of the general study design and/or type of methodology.

Your answer will help HSD in assigning applications to reviewers and in managing workload. Examples: a longitudinal observational study; a double-blind, placebo-controlled randomized study; ethnographic interviews; web scraping from a convenience sample of blogs; medical record review; coordinating center for a multi-site study.

This is a cluster-randomized controlled trial with FP clinics as the unit of randomization.

1.7 Intent. Check all the descriptors that apply to your activity. You must place an “X” in at least one box.

This question is essential for ensuring that your application is correctly reviewed. Please read each option carefully.

Descriptor
 1. Class project or other activity whose purpose is to provide an educational experience for the researcher (for example, to learn about the process or methods of doing research).
 2. Part of an institution, organization, or program's own internal operational monitoring.
 3. Improve the quality of service provided by a specific institution, organization, or program.
 4. Designed to expand the knowledge base of a scientific discipline or other scholarly field of study, and produce results that: 
• Are expected to be applicable to a larger population beyond the site of data collection or the specific subjects studied, or• Are intended to be used to develop, test, or support theories, principles, and statements of relationships, or to inform policy beyond the study.
 5. Develop information about a drug or device through its prospective use and assignment to subjects, which will then be submitted to the Food and Drug Administration (FDA) in support of a marketing or research application for an investigational drug or device, or for changes to the purpose, population, or dose for an already-approved drug or device.
 6. Focus directly on the specific individuals about whom the information or biospecimens are collected through oral history, journalism, biography, or historical scholarship activities, to provide an accurate and evidence-based portrayal of the individuals.
 7. A quality improvement or program improvement activity conducted to improve the implementation (delivery or quality) of an accepted practice, or to collect data about the implementation of the practice for clinical, practical, or administrative purposes. This does not include the evaluation of the efficacy of different accepted practices, or a comparison of their efficacy.
 8. Public health surveillance activities conducted, requested, or authorized by a public health authority for the sole purpose of identifying or investigating potential public health signals or timely awareness and priority setting during a situation that threatens public health.
 9. Preliminary, exploratory, or research development activities (such as pilot and feasibility studies, or reliability/validation testing of a questionnaire)
 10. Expanded access use of a drug or device not yet approved for this purpose

11. Use of a Humanitarian Use Device

12. Other. Explain:

1.8 Background, experience, and preliminary work. Answer this question only if your proposed activity has one or more of the following characteristics. The purpose of this question is to provide the IRB with information that is relevant to its risk/benefit analysis.

- Involves more than minimal risk (physical or non-physical)
- Is a clinical trial, or
- Involves having the subjects use a drug, biological, botanical, nutritional supplement, or medical device.

“Minimal risk” means that the probability and magnitude of harm or discomfort anticipated in the research are not greater than those ordinarily encountered in daily life or during the performance of routine physical or psychological examinations or tests.

a. Background. Provide the rationale and the scientific or scholarly background for your proposed activity, based on existing literature (or clinical knowledge). Describe the gaps in current knowledge that your project is intended to address.

Do not provide scholarly citations. Limit your answer to less than one page, or refer to an attached document with background information that is no more than three pages long.

[figure not shown]
1. Many women in Africa remain unaware of their HIV status.

In sub-Saharan Africa, 60% of the ~23 million people living with HIV are women (11). Over half of HIV-positive individuals remain unaware of their status, making it impossible to link them to services (10). Likewise, when women without HIV infection are not tested, opportunities to link them to HIV prevention services are missed. Addressing this HIV testing gap is among the most fundamental needs in global HIV treatment and prevention.

2. Family planning services are common in many African countries.

Demographic and health surveys from numerous African countries show that a high proportion of women access FP services, and that use of modern contraceptive methods continues to increase (6-9). In Kenya, 53% of currently married women and 61% of sexually active unmarried women reported using a modern method of contraception (9). Figure 1 illustrates the striking increase in contraceptive use in married women in Kenya between 1989 and 2014. Adult HIV prevalence is superimposed on the same figure (18-23). This illustrates that a large proportion of Kenyan women, including many who are

Figure 1: Proportion of Married Women in Kenya using Modern Contraception (blue bars) and National HIV Prevalence in Kenya (black line) from 1989-2014

HIV-positive, could be reached through universal HIV testing in FP clinics.

Integration sexual and reproductive health (SRH) services including FP with HIV services has been recognized as a key strategy for increasing access, uptake, quality, efficiency, and cost-effectiveness (14, 24). Integration and linkage of programs was emphasized in the US Government Global Health Initiative Strategy of 2010 (25).

3. There are advantages to linking HIV testing and family planning services.

From an HIV-prevention perspective, there are numerous reasons to link HIV testing to FP services. First, FP clinics have access to a large proportion of sexually active women. Second, integrating HIV testing into FP clinics opens the gateway for women to access prevention and treatment services (10). HIV-negative women may benefit from prevention strategies such as couples counseling and testing (26), condom use (27), pre-exposure prophylaxis (28), and treatment of positive partners (29). Likewise, HIV-positive women can decrease their risk of transmission to sex partners by taking ART (29-31). A third reason to integrate HIV testing and FP services is the potential to reduce mother-to-child transmission of HIV by preventing unwanted pregnancies in HIV-positive women (32). On the other hand, many HIV-positive women will eventually desire additional children (33-42). Women with HIV, their partners, and their infants can benefit from knowing their status prior to conception (43).

4. WHO supports integration of sexual and reproductive health with HIV services.

In 2009, WHO reviewed evidence on linkages between SRH and HIV services (1), highlighting promoting and inhibiting factors that will be useful in planning future studies including this one (Figure 2). The SRH services (FP, maternal & child healthcare, gender based violence prevention and management, and STD prevention and management) were linked to HIV services including prevention, education, counseling, testing, prevention of mother-to-child transmission (PMTCT), clinical care, psychosocial, and other services. While differences in target audiences, provider time constraints, and structural barriers can be problematic for some linkages (44- 47), WHO and several

Figure 2. Factors Promoting or Inhibiting Effective Linkages between HIV and FP Services (1)

Promoting Factors	Inhibiting Factors

Positive attitudes & good practices among providers & staffOngoing capacity buildingInvolvement of the community and government during planning and implementationSimple, easily applied additional services which add no costs to existing servicesNon-stigmatizing servicesMale partner inclusionEngagement of key populations	
Lack of commitment from stakeholdersNon-sustainable fundingClinics understaffed/low morale/high turnoverInadequate infrastructure, equipment, and commoditiesLack of male partner participationWomen not sufficiently empowered to make SRH decisionsCultural and literacy issuesAdverse social events/domestic violence incidenceStigma preventing clients from utilizing services

reviews have concluded that integration is beneficial and feasible (1, 12-14). Many reviews also conclude that more data on integration of SRH and HIV services are needed (12-14).

5. Provider-initiated testing and counseling is key to increasing HIV testing.

A recent report from Central Province, Kenya showed that following training on provider-initiated testing and counseling (PITC), the proportion of visits at which HIV testing was offered in FP clinics was higher in PITC clinics (35%) compared to clinics that continued to use a referral system for HIV testing (20%), $p<0.01$ (48). A separate study in Kenya found that integration of services was motivating for staff and distributed clinics' workload better (49). These findings are consistent with

those of a systematic review of PITC in low- and middle-income countries, which support PITC as an important intervention to increase HIV testing (50).

b. Experience and preliminary work. Briefly describe experience or preliminary work or data (if any) that you or your team have that supports the feasibility and/or safety of this study.

It is not necessary to summarize all discussion that has led to the development of the study protocol. The IRB is interested only in short summaries about experiences or preliminary work that suggest the study is feasible and that risks are reasonable relative to the benefits. Examples: You have already conducted a Phase 1 study of an experimental drug which supports the Phase 2 study you are now proposing to do; you have already done a small pilot study showing that the reading skills intervention you plan to use is feasible in an after-school program with classroom aides; you have experience with the type of surgery that is required to implant the study device; you have a study coordinator who is experienced in working with subjects who have significant cognitive impairment.

[name] leads the SAIA Trial (R01 HD075057), which aims to improve PMTCT services in Kenya, Mozambique, and Cote d' Ivoire by applying the SAIA approach proposed in the present application. The methods have been published following peer-review (51). Briefly, the SAIA intervention is used chronologically and iteratively to optimize PMTCT across the cascade (Figure 3). First, an Excel-based tool is used to analyze the facility's PMTCT cascade (54), identifying steps where optimization would have the greatest impact on overall performance. Second, sequential process flow mapping is performed (Figure 4). The map guides step 3, in which healthcare workers identify, define, and implement workflow adaptations to eliminate bottlenecks. Step 4 involves monitoring the effect of the adaptations using routinely collected data. In step 5, additional iterations of the analysis and improvement cycle are implemented (Figure 5). To date, 17 of 18 intervention facilities have accepted the intervention, and report ownership of the process. Over a 6-month period, sites have implemented an average of six interventions; 81% of interventions show some improvement in relieving bottlenecks. We have identified five broad categories of interventions: service reorganization, expanding patient knowledge, improving communication, improving data, and introducing new interventions (norms, treatments, modalities, technologies. Several key lessons have been learned from the process to date:

- GET LEADERS ON BOARD: Support from leadership is essential, and it may take time to get buy in
- ENGAGE SUPPORT STAFF: Community health workers support and sustain implementation
- GO FOR LOW HANGING FRUIT: Interventions that improve facility adherence to existing DOH norms
- KEEP IT SIMPLE: Implement 1-2 interventions at a time
- PUSH SYSTEMS THINKING: Effective continuous quality improvement must include user-friendly systems tools for use by frontline healthcare workers and managers

Figure 3: Iterative Systems Analysis & Performance Improvement

[figure not shown]

Figure 4: Sample of Initial Steps in Sequential Process Flow Map

[figure not shown]
[figure not shown]

Figure 5: Repeat Analysis & Improvement Cycles

1.9 Supplements. Check all boxes that apply, to identify Supplements you should complete and upload to the Supporting Documents SmartForm in **Zipline**.

This section is here instead of at the end of the form to reduce the risk of duplicating information in this IRB Protocol form that you will need to provide in these Supplements.

Check all That Apply	Type of Research	Supplement Name
	Department of Defense The research involves Department of Defense funding, facilities, data, or personnel.	ZIPLINE SUPPLEMENT: Department of Defense
	Department of Energy The research involves Department of Energy funding, facilities, data, or personnel.	ZIPLINE SUPPLEMENT: Department of Energy
	Drug, biologic, botanical, supplement Procedures involve the use of any drug, biologic, botanical or supplement, even if the item is not the focus of your research	ZIPLINE SUPPLEMENT: Drugs
	Emergency exception to informed consent Research that requires this special consent waiver for research involving more than minimal risk	ZIPLINE SUPPLEMENT: Exception from Informed Consent for Emergency Research (EFIC)
	Genomic data sharing Genomic data are being collected and will be deposited in an external database (such as the NIH dbGaP database) for sharing with other researchers	ZIPLINE SUPPLEMENT: Genomic Data Sharing
	Medical device Procedures involve the use of any medical device, even if the device is not the focus of your research, except when the device is FDA-approved and is being used through a clinical facility in the manner for which it is approved	ZIPLINE SUPPLEMENT: Devices
	Multi-site study (You are asking the UW IRB to review one or more sites in a multi-site study.)	ZIPLINE SUPPLEMENT: Participating Site in Multi-Site Research
	Participant results sharing Individual research results will be shared with subjects.	ZIPLINE SUPPLEMENT: Participant Results Sharing
	None of the above	

2 PARTICIPANTS

2.1 Participants. Describe the general characteristics of the subject populations or groups, including age range, gender, health status, and any other relevant characteristics.

The unit of study and eventual randomization unit are the family planning clinics themselves. In 2014, there were 194 FP clinics in Mombasa County. Forty-three were public, while 151 were private, but worked with the DOH to dispense FP products provided at no cost by the government. Clinics ranged

from dozens to hundreds of clients per month. In total, the county had 110,682 FP clients in 2014, of whom 38,418 were new (mean 21 new clients/clinic/month). About 10% of new visits were post-partum.

In addition to FP clinics, there will be in-depth interviews conducted with FP clinic managers. These will likely be adults >18 years of age and both male and female.

2.2 Inclusion and exclusion criteria. Describe the specific criteria you will use to decide who will be included in your study from among interested or potential subjects. Define any technical terms in lay language.

Inclusion and Exclusion Criteria:

Clinics will be enrolled in the study though clinic managers and clinic staff will consent to participate in in-depth interviews. A set of family planning clinics will be enrolled with the goal of having a wide range of clinic sizes, degree of urbanity and performance level of the clinic. If clinics plan to be closed during the study period, they will be excluded. Additionally, if clinics are unwilling to be randomized or to participate in the SAIA intervention/approach then they will be excluded.

2.3 Prisoners. IRB approval is required in order to include prisoners in research, even when prisoners are not an intended target population.

a. Will you recruit or obtain data from individuals that you know to be prisoners?

For records reviews: if the records do not indicate prisoner status and prisoners are not a target population, select "No". See the [WORKSHEET: Prisoners](#) for the definition of "prisoner".

	No
	Yes

→ If yes, answer the following questions (i – iv).

i. Describe the type of prisoners, and which prisons/jails:

ii. One concern about prisoner research is whether the effect of participation on prisoners' general living conditions, medical care, quality of food, amenities, and opportunity for earnings in prison will be so great that it will make it difficult for prisoners to adequately consider the research risks. What will you do to reduce the chances of this?

iii. Describe what you will do to make sure that (a) your recruitment and subject selection procedures will be fair to all eligible prisoners and (b) prison authorities or other prisoners will not be able to arbitrarily prevent or require particular prisoners from participating.

iv. If your research will involve prisoners in federal facilities or in state/local facilities outside of Washington State: check the box below to provide your assurance that you will (a) not encourage or facilitate the use of a prisoner's participation in the research to influence parole decisions, and (b) clearly inform each prisoner in advance (for example, in a consent form) that participation in the research will have no effect on his or her parole.

 Confirmed

b. Is your research likely to have subjects who become prisoners while participating in your study?

For example, a longitudinal study of youth with drug problems is likely to have subjects who will be prisoners at some point during the study.

	No
	Yes

→ If yes, if a subject becomes a prisoner while participating in your study, will you continue the study procedures and/or data collection while the subject is a prisoner?

	No
	Yes

→ If yes, describe the procedures and/or data collection you will continue with prisoner subjects

2.4 Protected populations. IRB approval is required for the use of the subject populations listed here. Check the boxes for any of these populations that you will purposefully include in your research. (In other words, being a part of the population is an inclusion criterion for your study.)

The WORKSHEETS describe the criteria for approval but do not need to be completed or submitted.

Population	Worksheet
 Children	WORKSHEET: Children
 Children who are wards	WORKSHEET: Children
 Fetuses in utero	WORKSHEET: Pregnant Women
 Neonates of uncertain viability	WORKSHEET: Neonates
 Non-viable neonates	WORKSHEET: Neonates
 Pregnant women	WORKSHEET: Pregnant Women

“Children” are defined as individuals who have not attained the legal age for consent to treatments or procedures involved in the research and its specific setting. This will vary according to the location of the research (that is, for different states and countries).

a. If you check any of the boxes above, use this space to provide any information you think may be relevant for the IRB to consider.

N/A

2.5 Native Americans or non U.S. indigenous populations. Will you actively recruit from Native American or non-U.S. indigenous populations through a tribe, tribe-focused organization, or similar community-based organization?

Indigenous people are defined in international or national legislation as having a set of specific rights based on their historical ties to a particular territory and their cultural or historical distinctiveness from other populations that are often politically dominant.

Examples: a reservation school or health clinic; recruiting during a tribal community gathering

	No
	Yes → If yes, name the tribe, tribal-focused organization, or similar community based organization. The UW IRB expects that you will obtain tribal/indigenous approval before beginning your research.

2.6 Third party subjects. Will you collect private identifiable information about *other individuals* from your subjects? Common examples include: collecting medical history information or contact information about family members, friends, co-workers.

"Identifiable" means any direct or indirect identifier that, alone or in combination, would allow you or another member of your research team to readily identify the person. For example, suppose that you are studying immigration history. If you ask your subjects several questions about their grandparents but you do not obtain names or other information that would allow you to readily identify the grandparents, then you are not collecting private identifiable information about the grandparents.

	No
	Yes → If yes, these individuals are considered human subjects in your study. Describe them and what data you will collect about them.

2.7 Number of subjects. Can you predict or describe the maximum number of subjects (or subject units) you need to complete your study, for each subject group?

Subject units mean units within a group. For most research studies, a group will consist of individuals. However, the unit of interest in some research is not the individual. Examples:

- Dyads such as caregiver-and-Alzheimer's patient, or parent and child
- Families
- Other units, such as student-parent-teacher

Subject group means categories of subjects that are meaningful for your research. Some research has only one subject group – for example, all UW students taking Introductory Psychology. Some common ways in which subjects are grouped include:

- By intervention – for example, an intervention group and a control group.
- By subject population or setting – for example, urban versus rural families
- By age – for example, children who are 6, 10, or 14 years old.

The IRB reviews the number of subjects you plan to study in the context of risks and benefits. You may submit a Modification to increase this number at any time after you receive IRB approval. If the IRB determines that your research involves no more than minimal risk: you may exceed the approved number and it will not be considered non-compliance. If your research involves more than minimal risk: exceeding the approved number will be considered non-compliance.

	No → If no, provide your rationale in the box below. Also, provide any information you can about the scope/size of the research. You do not need to complete the table.
--------------------------	--

Example: you may not be able to predict the number of subjects who will complete an online survey advertised through Craigslist, but you can state that you will post your survey for two weeks and the number who respond is the number who will be in your study.

Yes

→ If yes, for each subject group, use the table below to provide your estimate of the maximum desired number of individuals (or other subject unit, such as families) who will complete the research.

Group name/description	Maximum desired number of individuals (or other subject unit, such as families) who will complete the research
*For clinical trials: provide numbers for your site and for the study-wide total number	
Preliminary review of FP clinics	
Randomization of FP clinics	
In-depth interviews	

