While HIV testing in new clients is our primary outcome, we feel that a performance score incorporating both counseling and testing may provide a better baseline measure of performance. Nonetheless, we will also consider the individual *HIV Counseling* and *HIV Testing* scores if they do not tend to track together, and will adapt our randomization accordingly. If too few clinics perform any HIV counseling or testing, we will choose alternative measures of performance in the FP Register, such as recording of client number, client type (new/revisit), age, telephone number, and village/landmark. The rationale for conducting this initial step in 50 clinics, rather than just the 24 needed for completion of the RCT, is to provide a larger sample to enter the restricted randomization process. Preliminary examination of these data will allow us to fine-tune our choice of variables on which to balance the study arms and to optimize the planned length of outcome evaluation periods to capture sufficient endpoints. If any clinics seem inappropriate for participation (e.g. planned closure or unmatchable outliers), they may be removed prior to the randomization.

Aim 1:

In the 12 intervention facilities, the study team will first work with FP clinic staff and managers to identify one or more sets of best practices, which will help to guide the subsequent iterative process improvement steps. A combination of quantitative, qualitative, observation, and flow-mapping data will be used for this purpose

Quantitative data: We will collect data on health system factors that could influence facility performance. We will develop a standardized reporting form, refining assessment items according to current implementation experience, but expect to cover domains including commodities, facility characteristics, human resources, information systems, management, and structure of linkage to HIV

care.

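### Does the stated mean of 21 new clients per clinic per month, which the plan's own totals put at 16.5, upset the trial's size, timing or costing?

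*Combined protocol and SAP*

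**What the plan says.** Section 2.1 (Participants) sets the scene with 2014 county figures. It states "In 2014, there were 194 FP clinics in Mombasa County" and divides them by ownership: "Forty-three were public, while 151 were private". Clinic size is described loosely as ranging "from dozens to hundreds of clients per month", which refers to all clients. The paragraph then reports that "the county had 110,682 FP clients in 2014", "of whom 38,418 were new (mean 21 new clients/clinic/month", and closes the description with "About 10% of new visits were post-partum". It mentions no subset of reporting clinics and no part-year of data.

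Two other places could in principle draw on a per-clinic volume:

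- Section 5.1 (Preliminary Performance Review) says that data from the reviewed clinics will be used "to optimize the planned length of outcome evaluation periods to capture sufficient endpoints".
- Section 1.5 (Objectives, Aim 3) says "We will also estimate cost to scale up, and conduct a budget impact analysis" from the Department of Health's perspective.

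**The concern.** The clinic is the unit of randomization, and new clients (less those already known to be HIV-positive) form the denominator of the primary outcome. The 21 is the only numerical per-clinic volume of new clients in the document, so a reader may take it for the expected cluster size. It does not agree with the totals beside it.

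If someone planned from it, two things would go wrong. First, over a 3-month window (the one used in Figure 6 for the performance score) they would expect 3 × 21 = 63 new clients per clinic where the totals give 3 × 16.5 = 49.5. Over 24 clinics that is 1,512 against 1,188, and reaching 63 per clinic would take 63 / 16.5 = 3.8 months. Secondly, a scale-up estimate built by multiplying the mean back over the county would give 21 × 194 × 12 = 48,888 new clients a year, against the 38,418 reported.

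**Working it through.** **Inputs, all from section 2.1:** 194 clinics (43 public + 151 private = 194, so the split is consistent); 38,418 new clients in 2014; 110,682 clients in all; about 10% of new visits post-partum; stated mean 21.

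**Step 1. Try to reproduce the stated mean.** Formula: new clients / clinics / months.

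- 38,418 / 194 / 12 = 16.50. This is not 21, and rounding cannot close a gap of 4.5.
- Ratio: 21 / 16.50 = 1.273, so the stated mean is 27% above the figure from the totals.

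**Step 2. Look for a reading that gives 21.**

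| Reading | Calculation | Result |
|---|---|---|
| Thirteen 4-week periods | 38,418 / 194 / 13 | 15.2 |
| Leaving out 10% post-partum, all clinics | 0.9 × 38,418 / 194 / 12 | 14.9 |
| Leaving out 10% post-partum, private clinics | 0.9 × 38,418 / 151 / 12 | 19.1 |
| Public clinics as denominator | 38,418 / 43 / 12 | 74.5 |
| All clients rather than new | 110,682 / 194 / 12 | 47.5 |
| Private clinics as denominator | 38,418 / 151 / 12 | 21.2 |

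Only the last rounds to 21. Working backwards, 38,418 / 12 / 21 = 152.5 clinics. Allowing for rounding of the mean (20.5 to 21.5), the denominator lies between 149 and 156.

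**Step 3. Could 21 be a genuine mean for private clinics?** Then private clinics would have had 21 × 151 × 12 = 38,052 new clients. That leaves 38,418 − 38,052 = 366 for the 43 public ones, or 366 / 43 / 12 = 0.7 per clinic per month. Even at 20.5 the remainder is 38,418 − 37,146 = 1,272, or 2.5 per public clinic per month. New clients are 38,418 / 110,682 = 35% of all clients, so a clinic with two dozen clients a month would see about 8 new ones. The private-only reading therefore sits badly with the size range in the same paragraph. A wrong denominator, or a mean per reporting clinic with about 152 reporting, fits better. The document does not settle which.

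**Step 4. Trace where the 21 is used.**

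- *Sample size and power.* The document has no such calculation: no power, no intracluster correlation and no target difference. There is nothing to recompute.
- *Evaluation-period length.* Section 5.1 adjusts this after the register data of the reviewed clinics have been examined. The input is observed volume.
- *Randomization.* Section 5.1 balances the arms on new client volume and performance score. A county average plays no part.
- *Aim 3.* Section 5.1 draws costs from the study budget, expense reports, published labour costs, staff interviews and time-and-motion observation. It estimates the number of patients a clinic can support from staff interviews and available time. No step multiplies a mean volume by the number of clinics.

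**Step 5. Would 16.5 be a better planning figure?** Not for the trial. The 24 trial clinics are 24 / 194 = 12% of the county's clinics. They come from a purposive sample of large and small, public and private, urban to rural facilities, from which outliers and closing clinics may be removed. Their mean could lie on either side of 16.5.

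**The case for a change.** The best case for acting is that the error is certain, can be checked within one paragraph and costs one number or one clause to put right. The figure concerns the quantity that decides how much outcome data each cluster yields, and the length of the evaluation period is still open. Whichever explanation is true, the sentence needs either a different mean or a stated denominator.

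The arithmetic stands in full, and the text as printed is inconsistent. The consequence does not stand. The shortfall of 49.5 against 63 clients arises only if the team plans from the 2014 county mean, whereas the plan looks at actual clinic volumes first. The sentence about adjusting evaluation periods is thus the safeguard against this error. The inflated 48,888 arises only if an analyst rebuilds by multiplication a total that is already printed correctly next to the mean. Any loss of power would have to be worked out from an intracluster correlation and testing proportions that the document does not supply.

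Nor is it certain that the mean is the wrong number. If about 152 clinics reported, 21 is correct for those clinics and the missing item is the denominator.

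**Conclusion.** The mean of 21 is a clerical slip or an unstated denominator in background text. On the printed totals the county mean is 16.5, and 21 overstates it by 27%. That size assumes that 194 and 38,418 are both right and that every clinic contributed for 12 months.

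No change to the plan follows. No design, analysis or costing step in the document takes the 21 as an input, so the demonstrated effect on evaluation length, balance of the arms, outcome analysis and Aim 3 is nil. Fixing the evaluation period on 16.5 instead would be a step backwards, because the plan already provides for data from the candidate clinics themselves. A reader who wants county volume should use the 38,418 directly.
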